#### 7.3 Methods of analysis

The evaluation of the primary and secondary effectiveness endpoint(s) will be performed both in the Per-Protocol Set (PPS) and in the Full Analysis Set (FAS) for the initial treatment phase, and only for the FAS for the repeat phase.

Unless otherwise specified, all measurements will be summarized descriptively at each visit by treatment group.

In general, continuous variables will be summarized using the following descriptive summary statistics: number of observations, arithmetic mean, standard deviation, minimum, lower quartile, median, upper quartile, maximum. Categorical data will be described using absolute and relative frequencies by category. Shift tables will be provided, where appropriate. For assessments over time, mean values may be plotted to explore the trajectory over time. All descriptive summaries and plots will be based on in-trial data (i.e., without imputation) unless otherwise specified.

In addition, estimated treatment differences will be presented together with two-sided confidence intervals and corresponding p-values, if appropriate. A statistical analysis plan (SAP) will be written in

addition to the protocol, including a more technical and detailed elaboration of the statistical analyses. The SAP will be finalized before database lock.

## 7.3.1 Interim analysis

An interim analysis (IA) assessing the safety and effectiveness will be performed after all subjects have completed the follow-up visit 48 weeks after their last injection during the initial treatment phase (Visit 9 (SV1)).

Summary tables and subject data listings will be provided for the SAF and the FAS and all variables that are outlined in detail in the IA section of the final SAP.

The SAP has to be finalized prior to the IA database lock. The IA database will be cleaned and a data base lock prior to export for data analysis will be done.

#### 7.3.2 Final analysis

Final analysis will be done after completion of the investigation (i.e., Visit RT5) by all subjects.

#### 7.3.3 Subject disposition

Summary tables will be provided for the following subject characteristics:

- Number of subjects, both screened and received at least one administration of device, included in the study.
- Number of subjects by visit.
- Number of subjects included in the SAF, FAS and PPS.
- Number of subjects withdrawn from the study and the reason for withdrawal

Subjects who prematurely discontinue the investigation after receiving at least one dose of device will be defined as dropouts, see section 6.3.11.

#### 7.3.4 Demographics and baseline characteristics

Summary statistics for demographic and baseline characteristics, including age, gender, race/ ethnicity, and other relevant study entry criteria will be prepared for the SAF. In addition, demographic and baseline characteristics including age, gender, race/ ethnicity as well as injection equipment will be presented by study site.

#### 7.3.5 Medical and aesthetic procedures history

Medical history (incl. concomitant diseases) and aesthetic procedures history will be encoded using the Medical Dictionary for Regulatory Activities (MedDRA) system. These data will be presented for the SAF using frequency tables.

#### 7.3.6 *Prior and concomitant treatments*

Prior and concomitant treatments (medication / non-pharmacological procedures) will be coded using MedDRA and the WHO DRUG Global, respectively. These data will be presented for the SAF using frequency tables.

## 7.3.7 Effectiveness endpoints

#### Primary effectiveness endpoint

The PPS and the FAS will be both considered equally important for the primary analysis. The analysis of the primary endpoint will be performed on the PPS (primarily) and FAS. Confirmatory testing will be performed in a hierarchical ordering. Non-inferiority is demonstrated only if the results are consistent for both analysis populations.

Subjects with missing baseline MVDS score and / or missing MVDS score at Week 24 after last injection of the initial treatment phase will be considered as non-responders for the primary analysis on the FAS.

To calculate the primary outcome measure, the improvement over Baseline in the MVDS score assessed live by the blinded evaluator at the site at Week 24 after last injection of the initial treatment phase by subtracting the Midface Scale grade obtained at Baseline. The proportion of subjects with MVDS score improvement of  $\geq 1$  point will be then calculated for each treatment group.

The primary outcome measure for effectiveness will be evaluated by means of a one-sided two-group Farrington-Manning test of proportions with the following hypotheses:

- H0:  $pA pB \le d0$
- $\circ \qquad H1: pA pB > d0.$

At this, pA is the response rate for saypha® VOLUME Lidocaine and pB is the response rate for , and d0 equals to -0.1. Thus, a negative value for this difference means that the response rate of saypha® VOLUME Lidocaine is lower than the response rate for In addition to this, the response rates for both treatment groups along with their Clopper-

Pearson exact 95% CIs will be tabulated.

The study decision will be based on a Farrington-Manning-statistics with a one-sided type I error rate level of 0.025.

In addition, **sensitivity analyses** of the primary effectiveness endpoint will be performed on the FAS addressing the different reasons for non-adherence and covering the following aspects (among others) to underline the robustness of the results:

- Complete case analysis: In this analysis only those subjects will be included for whom the primary endpoint could be calculated;
- Subjects with non-allowed concomitant medication / treatments before Week 24 after last injection of the initial treatment phase may be regarded as non-responder.
- Multiple imputation under MNAR assumption for imputing missing MVDS scores at Week 24 assessed live by the blinded evaluator.

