Treatment occasions	Baseline treatment will be administered at Visit 2 (Day 0). Each eligible subject will receive either saypha® VOLUME Lidocaine or the same into the midface region, according to the randomization scheme.
	Touch-up treatment is optional and may be administered at
	
 
Visit 3 (Week 2; initial treatment phase: TUP1) and
 

	Visit RT2 (Week 2 after RT1; repeat-treatment phase: TUP2)
	or repeat-treatment, respectively. Decision on touch-up treatment is in the discretion of the treating investigator, but none of the exclusion criteria must be met. Touch-up treatment may be performed on one or both sides of the midface. In any case, it must be performed using the same device (either test device or comparator device) which was initially applied to the subject.
	Repeat-treatment is optional and may be administered once during the clinical investigation at Visit RT1 in eligible subjects using the saypha® VOLUME Lidocaine only (even if the subject was treated with the comparator device before).

ENDPOINTS	
Effectiveness endpoints	
 
General information on effectiveness endpoints
 
The subjects pain assessment, nasolabial folds, and the volumetric change measurement will be assessed and analyzed for the left and right side of the face separately.
 
All other endpoints will be assessed and analyzed globally (i.e., left and right side together / combined)
 
For MVDSS: Subjects are defined as a 'responder' if they are showing an ≥1 point improvement on the 5-point MVDSS, based on the respective score at a given visit relative to the respective baseline score. The grade assigned at the respective baseline visit (either Baseline visit or Visit RT1) will represent the baseline value for derivation of the responder status at a given visit during the initial treatment phase or repeat-treatment phase. Assessments will be evaluated by either the blinded evaluator at the site or by the central
 

Primary effectiveness endpoint	The percentage of responders on the 5-point MVDSS, based on the blinded evaluator's live assessment at Week 24 after last injection of initial treatment phase compared to the pre-treatment score at Baseline visit

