# Post-market study (CPH-401-201258, VINO)

VINO (CPH-401-201258) was a prospective, open-label, multicentre, post-market study evaluating the performance and safety of saypha® VOLUME Lidocaine for the correction of nasolabial folds (NLF).

In total, 62 Caucasian subjects were screened and included in the investigation, 61 of whom completed the investigation. One subject terminated the investigation early after Week 4. The study showed that the device is effective in reducing NLFs.

At the primary endpoint (Week 24 assessment) 95.1% in the ITT population and 94.1% in the PP population demonstrated  $\geq$ 1 grade improvement in their NLF severity based on the nasolabial folds severity rating scale (NLF-SRS) compared with the baseline status (Day 0). Similarly, the proportion of subjects (ITT) with a reduction (i.e., improvement) of  $\geq$ 1 NLF severity grade was 95.1% (ITT) and 94.1% (PP) at Week 4 and 87.1% (ITT) and 86.3% (PP) at Week 36/ET.

In addition, the proportion of subjects (ITT) with an improvement of the NLF severity based on the NLF-SRS by  $\geq$ 1 grade from Baseline to Week 24 was assessed by an independent reviewer of photographs as 98.4% in the ITT and 98.0% in the PP population.

Besides, the study investigated the aesthetic improvement using the GAIS, subject's satisfaction with the treatment and pain rating assessed by the subject. Results are given in the IB and have been published.[46]

saypha® VOLUME Lidocaine was shown to be safe and well tolerated when used for correction of nasolabial folds (see section 4.2.1 for details).

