# 5.3 Endpoints: Criteria for evaluation

#### 5.3.1 General information on effectiveness endpoints

- The subjects pain assessment, nasolabial folds, and volumetric change measurement will be assessed and analyzed for the left and right side of the face separately.
- All other endpoints will be assessed and analyzed globally (i.e., left and right side together / combined)
- For MVDSS in general: Subjects are defined as a 'responder' if they are showing an ≥1 point improvement on the 5-point MVDSS, based on the respective score at a given visit relative to the respective baseline score. The grade assigned at the respective baseline visit (either Baseline visit or Visit RT1) will represent the baseline value for derivation of the responder status at a given visit during the initial treatment phase or repeat-treatment phase. Assessments will be evaluated by either the blinded evaluator at the site or by the central independent blinded photographic reviewer.

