# 5.3.2 Primary effectiveness endpoint

The effectiveness of the investigational device will be evaluated using the following primary endpoint:

 The percentage of responders on the 5-point MVDSS, based on *the blinded evaluator's live* assessment at Week 24 after last injection of initial treatment phase compared to the pretreatment score at Baseline visit

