## 6.4.13 Midface Volume Deficit Severity Scale (MVDSS) - Grading of midface volume deficiency

The severity of midface deficit will be evaluated based on the Midface Volume Deficit Severity Scale (MVDSS), which is a validated 5-point rating scale ranging from grade 0 (none/minimal) to grade 4 (very severe).

The scale is briefly described in Table 20. The detailed MVDSS is provided in section 20.1.

 Table 20. Croma - Midface Volume Deficit Severity Scale (MVDSS)

**Note:** No separate assessments will be performed for the *right and left* midface region. Only subjects with approximately symmetrical deficit will be included into the study (see InC#2 in section 6.3.3), so the left and the right cheek will *not* be graded separately. If asymmetry emerges during follow-up, which is unlikely, the grade will be assigned according to the side with a larger deficit, and asymmetry will be

Clinical Investigation Plan CPH-301-201417 Version 7.0 - 15-MAY-2024 recorded as an AE. If InC#2 is violated and asymmetry is already present at Day 0, the grade will also be assigned according to the side with the larger deficit. The same applies to eligibility for repeat-treatment (see InC#1 in see section 6.3.5).

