## 7.1 Sample size and hypothesis

The primary outcome measures for effectiveness will be evaluated by means of a one-sided two-group Farrington-Manning test for the difference between proportions with the following hypotheses:

- H0:  $pA pB \le -10\%$
- H1: pA pB > 10%

At this, pA is the percent response rate for saypha® VOLUME Lidocaine based on the blinded evaluator's live assessment at Week 24 after last injection of initial treatment phase, while pB is the corresponding response rate for the saypha . Thus, a negative value for this difference means that the response rate of saypha® VOLUME Lidocaine is lower than the response rate for

The non-inferiority margin is -10%.

Further assumptions for sample size calculation:

- Response rate at Week 24 for saypha® VOLUME Lidocaine is 85.6%
- Response rate at Week 24 for the second se
- Randomization ratio 2:1

Based on these assumptions, 437 subjects (saypha® VOLUME Lidocaine: n=291,

 $\alpha$  of 2.5%. Assuming 10% exclusion from PPS results in 486 subjects to be randomized. Adding 6% screen failures yields approximately 516 subjects to be enrolled.

Concerning FAS, it is expected that only very few subjects will be regarded as non-responder due to missing data for the primary effectiveness endpoint. Response rates at Week 24 after last injection of the initial treatment phase may be slightly smaller than assumed above. Due to the increased sample size in the FAS (more than 10% compared to the PPS) it is expected that the power will be adhered as specified above.

Sample size calculation was done using SAS® version 9.4.

Approximately 300 subjects are estimated to qualify for repeat treatment.

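### Does the primary-endpoint calculation in section 7.3.7 score worsening as response, and does it rest on a baseline rating that is never taken?

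*Protocol*

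**What the plan says.** **Direction.** Section 7.3.7 (primary effectiveness endpoint), repeated in the synopsis, starts from the improvement over Baseline in the live MVDSS grade at Week 24. It says this is found "by subtracting the Midface Scale grade obtained at Baseline", without a main verb and without naming what the Baseline grade is taken from. The next sentence takes, in each group, the proportion of subjects whose improvement is at least one point. Section 6.4.13 describes the MVDSS as "a validated 5-point rating scale ranging from grade 0 (none/minimal) to grade 4 (very severe"; a lower grade is therefore better. Section 5.3.1 defines a responder as a subject "showing an ≥1 point improvement on the 5-point MVDSS", judged against the relevant baseline score.

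**Baseline.** Section 5.3.1 states: "The grade assigned at the respective baseline visit (either Baseline visit or Visit RT1) will represent the baseline value". Section 5.3.2 has the Week 24 score "compared to the pretreatment score at Baseline visit", and the synopsis agrees. Section 6.1.2 identifies the Baseline visit as Visit 2. Table 1 and section 6.5.2 list no live MVDSS rating at Visit 2. Table 1 and section 6.5.1 list it at Visit 1, up to 14 days earlier. Section 6.1.1 says that baseline severity is rated at Visit 1. Under the secondary endpoints, section 7.3.7 and the synopsis define baseline for the initial phase as the latest assessment preceding the first treatment.

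**The concern.** This is the trial's only confirmatory endpoint, so its derivation should be beyond doubt. The one term that the sentence names as subtracted is the Baseline grade, so the natural completion is Week 24 minus Baseline. On the MVDSS that difference is negative for a subject who improves. If the one-point threshold were applied to it as a signed quantity, subjects who deteriorated would count as responders and those who improved would not.

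The visit label adds a second doubt. In the primary analysis on the full analysis set, a subject without a baseline score is a non-responder. If baseline meant strictly a rating made at Visit 2, every subject whose Visits 1 and 2 fell on different days would lack one under the schedule.

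**Working it through.** **1. The two readings of the subtraction.** Inputs: eligible baseline grades B are 2 or 3 (section 6.3.3.1, criterion 2). Week 24 grades W are 0 to 4 (section 6.4.13). This gives 2 × 5 = 10 pairs.

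| B | W | W − B | B − W | W − B ≥ 1 | B − W ≥ 1 |
|---|---|---|---|---|---|
| 2 | 0 | −2 | 2 | no | yes |
| 2 | 1 | −1 | 1 | no | yes |
| 2 | 2 | 0 | 0 | no | no |
| 2 | 3 | 1 | −1 | yes | no |
| 2 | 4 | 2 | −2 | yes | no |
| 3 | 0 | −3 | 3 | no | yes |
| 3 | 1 | −2 | 2 | no | yes |
| 3 | 2 | −1 | 1 | no | yes |
| 3 | 3 | 0 | 0 | no | no |
| 3 | 4 | 1 | −1 | yes | no |

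The signed W − B rule takes 3 pairs, all worsenings. The B − W rule takes 5 pairs, all improvements. Two pairs are unchanged, and no pair meets both rules. The readings are opposites, so one of them must be excluded by the text.

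**2. Which reading the text supports.**

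- The threshold sentence in 7.3.7 and the definition in 5.3.1 both require an improvement of at least one point. Neither sets a signed difference at +1 or more. Subtracting Baseline from follow-up is the usual change from baseline; on this scale a one-point improvement is a change of −1. The contradiction arises only if the signed change replaces the word improvement.
- Section 7.1 plans with "Response rate at Week 24 for saypha® VOLUME Lidocaine is 85.6" per cent. Under the reversed reading, about 86 in 100 treated subjects would have to show a greater midface deficit after volume was added. That is not a possible planning assumption.
- Where section 3.2.1 reports an earlier study on a different severity scale, it equates a fall in grade with improvement: "the proportion of subjects (ITT) with a reduction (i.e., improvement) of" at least one grade. This says nothing about the MVDSS derivation, but it shows the same convention.

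**3. Which grade is the baseline.** Live ratings scheduled up to the first injection: Visit 1, one; Visit 2, none. The next one, at Visit 3, comes two weeks after that injection. Section 6.1.1 names Visit 1 for baseline severity, and the baseline rule (latest assessment before first treatment) selects the same rating. Section 6.4.13 asks for a rating before each treatment, but refers to Table 1, which places it at Visit 1. Table 1 also allows Visits 1 and 2 to be held together, in which case the label is exact. The rationale recorded for Amendment 5 explains the present baseline rule: some assessments are made at Screening and not at Visit 2. One scheduled value and one rule that selects it leave nothing to choose.

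**4. Effect on the design figures.** 437 / (1 − 0.10) = 485.6, rounded up to the stated 486 randomized. Neither this figure, the −10% margin nor the one-sided 0.025 level depends on how the subtraction is written or on the name of the baseline visit.

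**The case for a change.** The strongest case for an edit is that the protocol itself states the arithmetic for its sole confirmatory endpoint, so this is not a detail left to the statistical analysis plan. The same broken sentence stands in two places. The sponsor corrected the baseline rule in 7.3.7 and the synopsis because of Screening assessments, but left the Baseline visit label in 5.3.1, 5.3.2 and the synopsis endpoint ("compared to the pre-treatment score at Baseline visit"). Section 7.7 requires a protocol amendment for a departure that affects the effectiveness analysis, so the governing text should be correct. The rule that scores a missing baseline as non-response makes it matter which rating is meant.

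The factual part stands: the sentence is incomplete, the label is loose, and the clarifying rule sits under the secondary-endpoint heading. The consequence does not. That rule is worded for the whole initial-treatment follow-up and is not limited to secondary endpoints. An analyst who uses the Visit 1 grade and counts a fall of one grade or more as response is following the plan, so section 7.7 is not engaged. Nor does a Visit 1 rating leave the baseline missing. Rewording also carries a small risk. Section 5.3.1 covers the Visit RT1 baseline and the photographic reviewer as well, so text tied to the Visit 1 live rating would be wrong there.

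**Conclusion.** The concern does not call for a change. What remains is clerical: a sentence without a verb or a stated order of subtraction, and a visit label that is inexact when Screening and Baseline fall on different days. Only one direction and one baseline grade are consistent with the document, so no subject's responder status, no sample-size figure and no conclusion alters. The 3-against-5 pair count measures the gap to a reading that no analyst following sections 5.3.1 and 7.3.7 would adopt.

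This rests on two assumptions: that the live rating is made as Table 1 schedules it, once before the first injection, and that the word improvement keeps its plain meaning on a severity scale. Both are supported by the text.

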In addition, at least the following main secondary effectiveness endpoints will be compared between the treatment groups by means of 95% confidence intervals for the differences in

- proportion of subjects with response on the MVDSS as assessed by the blinded evaluator at the site
- proportion of subjects with response on the MVDSS as assessed by the independent blinded photographic reviewer
- mean change in midface volume deficit measured on the 5-point MVDSS and based on the blinded evaluator's live assessment
- proportion of subjects with global aesthetic improvement (in modified GAIS) as assessed by the subject
- proportion of subjects with global aesthetic improvement (in modified GAIS) as assessed by the blinded evaluator

This will be done for each time of assessment during follow-up for initial treatment.

The resulting 95% confidence intervals for proportions will be presented in forest plots and the boundaries of the confidence intervals evaluated with respect to their clinical relevance in an exploratory manner.

The investigational device during repeat-treatment phase (saypha® VOLUME Lidocaine) will be evaluated descriptively using the following other endpoints:

- The percentage of responders on the 5-point MVDSS, based on the *blinded evaluator's live* assessment at Week 4, 12 and 24 after last injection of repeat-treatment phase compared to the score at Visit RT1
- Mean change in midface volume deficit measured on the 5-point MVDSS and based on the blinded evaluator's live assessment at Week 4, 12, and 24 after last injection of repeat-treatment phase compared to the score at Visit RT1
- Shift from baseline (Visit RT1) in NLF-SRS based on the blinded evaluator's live assessment at Week 4, 12 and 24 after last injection during repeat-treatment phase
- The extent of subject's satisfaction with overall treatment outcome at Week 4, 12 and 24 after last injection of repeat-treatment phase as assessed by the subject using the Face-QTM Questionnaire "Satisfaction with Outcome"

- The extent of subject's appearance appraisal at Week 4, 12 and 24 after last injection of repeattreatment phase as assessed by the FACE-QTM questionnaire "Satisfaction with Cheeks" compared to the score at Visit RT1
- Subject evaluation of pain after each treatment (repeat and touch-up-treatment) on an 11-point scale, where 0 is no pain and 10 is the worst pain imaginable

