#### 7.3.9 Multicentre trial

This study will take place in approximately 16 investigation sites. Inclusion of subjects is planned to be as equally distributed as possible between the sites (see section 6.3.1 for details).

Possible country (or geographical cluster) and study site effects will not be included in the primary analysis, but will be evaluated on an exploratory level by tabulation of the primary and key secondary endpoints by country (or geographical cluster) and study site, respectively.

Any pooling of study sites with few subjects as well as pooling of countries in geographical clusters will be agreed and specified in the SAP before database lock.

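### The primary non-inferiority test is unadjusted, and no listed analysis adjusts for baseline MVDSS grade (2 v 3): a modest, nearly free gain in efficiency and robustness, not an error

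*Protocol*

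**What the plan says.** Protocol section 7.3.7 fixes the confirmatory analysis: "The primary outcome measure for effectiveness will be evaluated by means of a one-sided two-group Farrington-Manning test of proportions". It adds: "The study decision will be based on a Farrington-Manning-statistics with a one-sided type I error rate level of 0.025". The test is run on the PPS and the FAS, and both must agree. FAS subjects without a baseline or Week 24 score count as non-responders. Three sensitivity analyses are listed (complete cases, prohibited treatments as non-response, multiple imputation under MNAR), and the list is expressly not exhaustive. None of the three adjusts for a baseline variable.

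Other places that bear on this:
- Sections 6.3.3.1 and 5.3.1: entry requires MVDSS grade 2 or 3 from the blinded evaluator, and a responder improves by at least 1 point on that baseline grade.
- Section 7.9: permuted blocks at 2:1, with no stratification factor named.
- Section 7.3.10: exploratory logistic models for equipment, gender, skin type, race and ethnicity, and age. Baseline grade is not among them.
- Section 7.3.7, secondary endpoints: a 95% confidence interval for the difference in "mean change in midface volume deficit measured on the 5-point MVDSS", exploratory, with no model named.
- Section 7.7: a deviation that affects the effectiveness analysis needs a protocol amendment.

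**The concern.** Scoring response against baseline does not adjust for baseline. The chance of a 1-point improvement can still differ between subjects who start at grade 2 and at grade 3. If it does, an unadjusted difference in proportions carries between-grade variation that a stratified estimate removes, whichever grade responds better. If the arms happened to differ in grade mix, the planned outputs would also contain no adjusted estimate to show whether the conclusion depends on it.

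At stake is a little power in a trial planned at about 83% that must succeed in two analysis sets, and a ready answer to a predictable question about baseline balance. Section 6.1.3 leaves the sponsor and the CRO biostatistician unblinded, so an adjustment chosen after an imbalance is seen would be open to challenge. That is the main reason to fix one in advance.

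**Working it through.** **Inputs from the protocol.** Section 7.1 states "The non-inferiority margin is -10" (percent), "Response rate at Week 24 for saypha® VOLUME Lidocaine is 85.6" (percent) and "Randomization ratio 2:1". It gives 437 evaluable subjects, 291 on the test device, hence 437 - 291 = 146 on the comparator. The one-sided level is 0.025.

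**Assumptions.** The comparator response rate is blacked out in the public text. I take 85.6%: of the values tried between 84% and 87%, only this one returns 291/146. The share at grade 3 (f) and the response gap between grades (g) are not in the protocol. I use f = 0.3 to 0.5 and g = 0 to 20 points.

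**Step 1: the plan's own figures.** With p = 0.856, p(1-p) = 0.1233. At 80% power with unpooled variance, comparator n = 0.1233 x (1 + 1/2) x (1.960 + 0.842)^2 / 0.10^2 = 145.12, so 146. Test n = 2 x 145.12 = 290.2, so 291. The total is 437, as stated, and 437/0.9 = 485.6, so 486 randomised.

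Farrington-Manning power at 291/146:
- SE under the alternative: s1 = sqrt[0.1233 x (1/291 + 1/146)] = 0.0356.
- SE restricted to the -10% null (rates 0.808 and 0.908): s0 = 0.0333.
- Power = Phi[(0.10 - 1.96 x 0.0333)/0.0356] = 83.6%, or 84.4% by exact enumeration.

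The Amendment 5 entry (section 19.5) gives a power above 83%, so this agrees. Exact type I error at the boundary is about 0.027 (0.756 v 0.856, and 0.80 v 0.90), close to nominal.

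**Step 2: gain from stratifying by grade.** The share of outcome variance between grades is R2 = f(1-f)g^2 / [p(1-p)], and the SE is multiplied by sqrt(1 - R2). For f = 0.5 and g = 0.10: R2 = 0.25 x 0.01 / 0.1233 = 0.020. Power follows from Step 1 with both SEs scaled.

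| Response gap | Variance gain (f = 0.3 to 0.5) | SE factor | Power | Equivalent subjects of 437 |
|---|---|---|---|---|
| 0 | 0% | 1.000 | 83.6% | 0 |
| 5 points | 0.4-0.5% | 0.998-0.997 | 83.7-83.8% | about 2 |
| 10 points | 1.7-2.0% | 0.991-0.990 | 84.2-84.3% | 7-9 |
| 20 points | 6.8-8.1% | 0.965-0.959 | 85.9-86.4% | 30-35 |

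**Step 3: chance imbalance.** The SD of the arm difference in grade-3 share is sqrt[f(1-f)(1/291 + 1/146)] = 4.6 to 5.1 points. A 1-SD imbalance moves the risk difference by g times that: about 0.5 point at a 10-point gap and 0.9-1.0 point at a 20-point gap. The SE of the difference is 3.6 points and the margin is 10. This is the same quantity as in Step 2: for f = 0.5 and g = 0.20, (0.0101/0.0356)^2 = 0.081, which equals R2.

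**The case against.** The strongest reply is that nothing is wrong. The unadjusted test is valid, it reproduces the stated sample size and power, and its type I error is close to nominal. Section 7.3.7 leaves room for further sensitivity analyses, so the SAP may already contain an adjusted one. This stands, and it limits the point to a free improvement.

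A reader might infer more, in ways the protocol does not support:
- **That imbalance biases the primary result.** Under randomisation it is part of the crude SE. Step 3 shows that it is the same component as the precision loss, so the two must not be counted twice.
- **That grade 3 subjects have more room to respond.** The scale runs from 0 to 4, so a grade 2 subject has two grades of room and needs one. Volume is chosen by severity and touch-up is allowed (sections 6.2.2 and 6.2.3), which may even out response. A gap of zero is possible.
- **That baseline is ignored, or known for everyone.** Baseline defines the endpoint, MVDSS shift tables are planned, and section 7.3.7 provides for missing baseline scores.
- **That the mean-change comparison is unadjusted.** Section 7.3.7 asks only for a confidence interval and names no model. ANCOVA could supply it.

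Replacing the primary test is also not a mere wording change. Section 19.5 indicates that recruitment is complete, staff are unblinded, and section 7.7 would require an amendment.

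**Conclusion.** The point holds in a limited form. The protocol fixes an unadjusted primary test and lists no analysis that adjusts for baseline MVDSS grade, a two-level pre-treatment variable already collected and tied to the endpoint. The variance gain is 0% with no response gap, about 2% at 10 points (under 1 power point), and 7-8% at 20 points (about 2.5 to 3 power points). These sizes rest on the assumed grade split, the assumed gap and a comparator rate taken as 85.6%. Neither the validity of the confirmatory test nor the 437 is in question.

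**What to change.** Keep the hypotheses, the -10% margin, one-sided 0.025 and N = 437. Before the interim database lock, pre-specify a risk difference stratified by baseline MVDSS grade (2 v 3), with Mantel-Haenszel weights and a score-type (Miettinen-Nurminen or Farrington-Manning) interval, on PPS and FAS, read against the same margin. The simpler course is to name it the main supportive analysis. Making it the primary test is possible, but only by protocol amendment under section 7.7.

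State a rule for FAS subjects without a baseline score, for example that they stay non-responders and are placed in the more frequent grade. Optionally, the SAP can use baseline grade as a covariate in the exploratory mean-change interval.

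As a supportive analysis the cost is a few lines of text and one more table: no new data and no more subjects.
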